13.3.2 Adverse Events and Toxicity Data

Adverse events (AEs): All adverse events recorded during the trial will be summarized. The incidence of treatment-emergent adverse events will be summarized according to primary system organ class, severity (based on the National Cancer Institute's Common Terminology Criteria for Adverse Events (CTCAE) version 4.0), type of adverse event, and relationship to treatment. Deaths reportable as SAEs and non-fatal serious adverse events will be listed by patient and tabulated by primary system organ class, and type of adverse event. Any other information collected (e.g. start/end dates, cumulative dose/number of cycles of therapy, duration of adverse event, severity, or relatedness to trial medication) will be listed, as appropriate.

Laboratory abnormalities: The frequency of notable lab abnormalities (i.e., newly occurring CTCAE grade-3 or -4 laboratory toxicities), will be displayed by parameter and treatment cycle. Similarly, the frequency of all laboratory abnormalities will be displayed by parameter, worst CTCAE grade experienced, and treatment cycle. A separate listing will display notable laboratory abnormalities (i.e., newly occurring CTCAE grade-3 or -4 laboratory toxicities).

Study Participant Self-Administration Drug Diary**DFCI Study Number:**

Participant Name: _____

Your Doctor _____ Phone _____

Your Nurse _____ Phone _____

Dosing Instructions for Study Drug:

Your dose of Trametinib is _____ mg made up of _____ - _____ mg tablets.

Your dose of INCB039110 is _____ mg made up of _____ - _____ mg tablets.

Your dose of Dabrafenib is _____ mg made up of _____ - _____ mg capsules.

- You will take trametinib once per day in the morning. You will take INCB039110 once per day in the morning. You will take dabrafenib twice per day, once in the morning and then twelve hours later.
- Pills need to be taken without food on an empty stomach, at least 1 hour prior to a meal and 2 hours after a meal. Pills can be taken with water.
- Pill cannot be crushed, chewed or dissolved in water.
- Dabrafenib, INCB039910 and Trametinib may be taken together.
- Vomited doses should not be made up.
- Missed doses should not be made up if more than 6 hours have lapsed from the scheduled/planned dose time.
- Each of the study drugs should be kept in the original container they are distributed in.
- Please remember to bring any unused drug, all empty containers, and your drug diary to your clinic visits.
- Please contact your study staff immediately if you develop a fever, which is defined as a temperature of 38.5 Celsius or 101.3 Fahrenheit
- Dabrafenib and INCB039110 should be stored at room temperature. Trametinib should be refrigerated.

- Wash your hands with soap and water after taking your dose

DOSING LOG: Cycle ____ Date of Day 1: _____

Dosing Log Instructions

- Make sure to indicate the date, time, amount taken and any comments immediately following each dose.
- Bring your study drug containing all remaining medication, including empty bottles, to each visit.
- Once complete, provide this signed or initialed and dated dosing log to your study doctor or nurse.

Day	Date	Time of Trametinib Dose	# Tablets	Time of INCB039110 Dose	# Tablets	Time of Morning Dabrafenib Dose	# Capsules	Time of Evening Dabrafenib Dose	# Capsules	Comments If dose was vomited, missed or skipped, indicate reason below.
1		 am  pm		 am  pm		 am  pm		 am  pm		
2		 am  pm		 am  pm		 am  pm		 am  pm		
3		 am  pm		 am  pm		 am  pm		 am  pm		
4		 am  pm		 am  pm		 am  pm		 am  pm		
5		 am  pm		 am  pm		 am  pm		 am  pm		
6		 am  pm		 am  pm		 am  pm		 am  pm		
7		 am  pm		 am  pm		 am  pm		 am  pm		
8		 am  pm		 am  pm		 am  pm		 am  pm		
9		 am  pm		 am  pm		 am  pm		 am  pm		
10		 am  pm		 am  pm		 am  pm		 am  pm		
11		 am  pm		 am  pm		 am  pm		 am  pm		
12		 am  pm		 am  pm		 am  pm		 am  pm		

Day	Date	Time of Trametinib Dose	# Tablets	Time of INCB039110 Dose	# Tablets	Time of Morning Dabrafenib Dose	# Capsules	Time of Evening Dabrafenib Dose	# Capsules	Comments If dose was vomited, missed or skipped, indicate reason below.
13		 am  pm		 am  pm		 am  pm		 am  pm		
14		 am  pm		 am  pm		 am  pm		 am  pm		
15		 am  pm		 am  pm		 am  pm		 am  pm		
16		 am  pm		 am  pm		 am  pm		 am  pm		
17		 am  pm		 am  pm		 am  pm		 am  pm		
18		 am  pm		 am  pm		 am  pm		 am  pm		
19		 am  pm		 am  pm		 am  pm		 am  pm		
20		 am  pm		 am  pm		 am  pm		 am  pm		
21		 am  pm		 am  pm		 am  pm		 am  pm		
22		 am  pm		 am  pm		 am  pm		 am  pm		
23		 am  pm		 am  pm		 am  pm		 am  pm		
24		 am  pm		 am  pm		 am  pm		 am  pm		
25		 am  pm		 am  pm		 am  pm		 am  pm		
26		 am  pm		 am  pm		 am  pm		 am  pm		
27		 am  pm		 am  pm		 am  pm		 am  pm		
28		 am  pm		 am  pm		 am  pm		 am  pm		

APPENDIX D

PREGNANCY REPORT FORM

PREGNANCY INFORMATION FAX FACSIMILE TRANSMISSION			Study #: _____
Ticket Number: _____			SAE [contact]
Initial Report Date: _____			Follow-up Report Date: _____
Principal Investigator:			Reporter:
Reporter Telephone #:			Reporter FAX #:
   <small>Investigator Number</small>		   <small>Subject Number</small>	
<small>Complete all of the investigator and subject number boxes provided. Use leading zeros, when necessary, to complete all expected boxes.</small>			<small>Record the first letter of the subject's first, middle and last name, in that sequence. If the subject has no middle name, enter a dash.</small>
<small>Example: Investigator #407 would be filled in as:</small>  0  0  4  0  7			<small>Example: A - C</small>
Subject's Sex:		Subject's Weight:	
 Female  Male		<small>kg</small>	
Subject's Date of Birth:		<small>DD - MMM - YYYY</small>	
Subject's Ethnicity (check one only):  Hispanic or Latino  Not Hispanic or Latino  Not Available			
Subject's Race (check all that apply):  American Indian or Alaska Native  Asian  Black or African American  Native Hawaiian or Other Pacific Islander  White  Not Available			
Study Drug:		Study Drug Start Date: _____	
Study Drug Stop Date: _____		<small>DD - MMM - YY</small>	
OR		 Study Drug Continuing	
Dose:	Route: ORAL	Frequency: QD	Kit #:
First Day of Last Menstrual Period: _____		Estimated Date of Delivery: _____	
<small>Method of Contraception (check all that apply):</small>  Oral Contraceptive Pills  Condoms  Periodic Abstinence  Progestin Injection or Implants  Spermicide  Diaphragm  Intrauterine Device (IUD)  Tubal Ligation  Other, specify: _____			
<small>Reproductive History:</small>  Gravida _____  Para _____			
<small>Tests performed during pregnancy:</small>  None  Unknown			
 CVS Results:  Normal  Abnormal		 Amniocentesis Results:  Normal  Abnormal	
 Ultrasound Results:  Normal  Abnormal			
Pregnancy Outcome			
<small>Was pregnancy interrupted?</small>  Yes  No <small>If yes, specify:</small>  Elective Termination  Spontaneous Abortion  Ectopic			
<small>Date of Termination:</small> _____			
<small>If pregnancy was not terminated, specify pregnancy outcome (and provide infant outcome information)</small>			
 Vaginal Birth:  Premature		<small>OR</small>  C-Section:  Scheduled  Term  Emergency	
<small>Date of Delivery:</small> _____			
<small>Infant outcome information:</small>  Normal  Abnormal			
<small>Additional Case Details (if needed):</small>			
<small>NOTE: For an initial reporting fax both the Pregnancy Report CRF and Additional Pregnancy Information Fax Page. For follow-up reporting, fax only the Additional Pregnancy Information Fax Page.</small>			

APPENDIX E**CONCOMITANT MEDICATIONS AND NON-DRUG THERAPIES****1.1. Permitted Medications and Non-Drug Therapies**

The investigator must be informed as soon as possible about any medication taken from the time of screening until 30 days after the last dose of study treatment. Any concomitant medication(s), including dietary supplements, taken during the study will be recorded in the eCRF. The minimum requirement is that drug name, dose, and the dates of administration are to be recorded. Additionally, a complete list of all prior surgical procedures will be recorded in the eCRF.

Subjects should receive full supportive care during the study, including transfusions of blood and blood products, and treatment with antibiotics, anti-emetics, anti-diarrheals, and analgesics, and other care as deemed appropriate, and in accordance with their institutional guidelines. Use of anticoagulants such as warfarin is permitted provided that INR is monitored in accordance with local institutional practice.

1.2. Prohibited Medications and Non-Drug Therapies

The use of certain medications and illicit drugs within 28 days or 5 half lives, whichever is shorter, prior to registration and for the duration of the study will not be allowed.

The following medications or non-drug therapies are also prohibited while on treatment in this study:

- Other anti-cancer therapies;
- Other investigational drugs;
- Antiretroviral drugs (Note: Subjects with known HIV are ineligible for study participation);
- Herbal remedies (e.g., St. John's wort);
- Dabrafenib is metabolized primarily by Cytochrome P450 (CYP) 2C8 and CYP3A4. Co-administration of dabrafenib with ketoconazole, a CYP3A4 inhibition, or with gemfibrozil, a CYP2C8 inhibitor, resulted in increases in dabrafenib AUC of 71% and 47%, respectively. Drugs that are strong inhibitors or inducers of CYP3A and CYP2C8 (see list in Table 1) may only be used under special circumstances (e.g. as a single use for a procedure) while treatment with study drug is interrupted as they may alter dabrafenib concentrations; consider therapeutic substitutions for these medications. The list may be modified based on emerging data. Refer to the SPM for the most current list.

Table 1 Prohibited Medications

PROHIBITED – strong inducers of CYP3A or CYP2C8, since concentrations of dabrafenib may be decreased	
Class/Therapeutic Area	Drugs/Agents
Antibiotics	Rifamycin class agents (e.g., rifampin, rifabutin, rifapentine),
Anticonvulsant	Carbamazepine, oxcarbazepine, phenobarbital, phenytoin, s-mephentoin
Miscellaneous	bosentan, St. John's wort

PROHIBITED – Strong inhibitors of CYP3A, or CYP2C8 since concentrations of dabrafenib may be increased	
Class/Therapeutic Area	Drugs/Agents
Antibiotics	Clarithromycin, telithromycin, troleandomycin
Antidepressant	Nefazodone
Antifungals	Itraconazole, ketoconazole, posaconazole, voriconazole
Hyperlipidemia	Gemfibrozil
Antiretroviral	ritonavir, saquinavir, atazanavir
Miscellaneous	Conivaptan

1.3. Medications to be Used with Caution

The following medications should be used with caution as their concentrations may be altered by dabrafenib or they may alter dabrafenib concentrations:

- Drugs that are moderate inhibitors or inducers of CYP3A and CYP2C8 as they may alter concentrations of dabrafenib.
- Dabrafenib has been shown to induce CYP3A4 and CYP2C9 in vivo using midazolam (CYP3A4 substrate) and S-warfarin (CYP2C9 substrate). Dabrafenib is an in vitro inducer of CYP2B6 and other enzymes such as CYP2C8, CYP2C19, UDP-glucuronyl transferases. Transporters may also be affected. Co-administration of dabrafenib and medications which are affected by the induction of these enzymes (including warfarin) and transporters may result in loss of efficacy. If co-administration of these medications is necessary, investigators should monitor subjects for loss of efficacy or consider substitutions of these medications. A partial list of these medications is provided in

Table 2 and in the SPM.

- Therapeutic level dosing of warfarin can be used with close monitoring of PT/INR by the site. Exposure decreased by 37% due to enzyme induction when on treatment, thus warfarin dosing may need to be adjusted based upon PT/INR. Consequently, when discontinuing dabrafenib, warfarin exposure may be increased and thus close monitoring via PT/INR and warfarin dose adjustments must be made as clinically appropriate. Prophylactic low dose warfarin may be given to maintain central catheter patency.

Dabrafenib solubility is pH-dependent with decreased solubility at higher pH. Drugs such as proton pump inhibitors that inhibit gastric acid secretion to elevate gastric pH may decrease the solubility of dabrafenib and reduce its bioavailability. No clinical study has been conducted to evaluate the effect of pH on dabrafenib pharmacokinetics. In an ad-hoc analysis, no differences in C_{max} and AUC were noted between subjects who reported taking pH-elevating products relative to other subjects. Due to the theoretical risk that pH-elevating agents may decrease oral bioavailability and

exposure to dabrafenib, these medicinal products that increase gastric pH should be used with caution when administered with dabrafenib

Table 2 Medications to be used with Caution

USE WITH CAUTION: Moderate inhibitors of CYP3A, or CYP2C8 since concentrations of dabrafenib may be increased	
Class/Therapeutic Area	Moderate CYP3A and CYP2C8 Inhibitors
Antiarrhythmics	Diltiazem, verapamil
Antibiotic	Erythromycin
Antifungal	Fluconazole
Miscellaneous	Aprepitant
USE WITH CAUTION: Co-administration of these drugs with study treatment may result in loss of efficacy. Monitor subjects for loss of efficacy or substitute with another medication.	
Class/Therapeutic Area	CYP3A4, CYP2B6, CYP2C8, CYP2C9, or CYP2C19 Substrates that May be Affected by Induction
Analgesics	Alfentanil, buprenorphine, celecoxib, codeine, fentanyl, methadone, oxycodone
Antiarrhythmics	Disopyramide, dronedarone, mexiletine, propafenone, quinidine
Antibiotics	Chloramphenicol, doxycycline, erythromycin, moxifloxacin
Anticoagulants/ Antiplatelets	Cilostazole, warfarin
Anticonvulsants	Divalproex, lamotrigine, valproate, zonisamide
Antidepressants and Antipsychotics	Aripiprazole, bupropion, buspirone, desipramine, haloperidol, mirtazapine, pimozide, quetiapine, trazodone, amitriptyline, clomipramine, imipramine
Antidiabetics	Glyburide, saxagliptin, tolbutamide, nateglinide, pioglitazone, repaglinide, rosiglitazone
Antifungals	Caspofungin, fluconazole, terbinafine
Antihistamines	Astemizole, chlorpheniramine, ebastine
Antihypertensives	Amlodipine, diltiazem, felodipine, nifedipine, nilvadipine, nisoldipine, verapamil
Antimigraine Agents	Diergotamine, eletriptan, ergotamine
Corticosteroids	Dexamethasone, methylprednisolone, oral budesonide
Erectile Dysfunction Agents	Sildenafil, tadalafil, vardenafil
HMG-CoA Reductase Inhibitors	Atorvastatin, lovastatin, simvastatin
Hypnotics and Sedatives	Alprazolam, brotizolam, diazepam, estazolam, midazolam, triazolam, zolpidem, zopiclone
Immunosuppressants	Everolimus, sirolimus, tacrolimus
Miscellaneous	Aprepitant, cisapride, darifenacin, disopyramide, leflunomide, methohexitol, oral contraceptives, quinine, ranitidine, solifenacin, sulfasalazine, tramadol, tolvaptan, chloroquine, zopiclone
Selective Aldosterone Blockers	Eplerenone

USE WITH CAUTION: Co-administration of drugs that increase gastric pH should be used with caution when administered with dabrafenib..

pH altering agents	dexlansoprazole, esomeprazole, famotidine, ilaprazole, lansoprazole, omeprazole, pantoprazole, rabeprazole, ranitidine
--------------------	--

Abbreviations: CYP = cytochrome P450; HMG-CoA = 3-hydroxy-3-methylglutaryl-coenzyme A.

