3.1.5 Age ≥ 18 years. Because no dosing or adverse event data are currently available on the use of INCB039110 in combination with dabrafenib and trametinib in patients < 18 years of age, children are excluded from this study, but will be eligible for future pediatric trials.

3.1.6 ECOG performance status ≤ 1 (Karnofsky $\geq 70\%$, see Appendix A).

3.1.7 Life expectancy of greater than 3 months in the opinion of the investigator.

3.1.8 Patients must have acceptable organ and marrow function as defined below:

– Leukocytes (WBCs)	$\geq 3,000/\mu\text{L}$
– absolute neutrophil count	$\geq 1,500/\mu\text{L}$
– hemoglobin	$\geq 9 \text{ g/dL}$ (patients may be transfused to this level)
– platelets	$\geq 100,000/\mu\text{L}$
– total bilirubin	$< 1.5 \times$ institutional upper limit of normal

OR

- AST(SGOT)/ALT(SGPT)	> 1.5 x institutional upper limit of normal allowed if direct bilirubin is within normal range.
- PT/INR and PTT	$\leq 2.5 \times$ institutional upper limit of normal
- Serum creatinine	$< 1.3 \times$ ULN ¹ $\leq 1.5 \text{ mg/dL}$ OR creatinine clearance $\geq 50 \text{ mL/min/1.73 m}^2$
- Potassium	$> 3 \text{ and } < 5.5 \text{ mmol/L}$
- Magnesium	$> 1.2 \text{ and } < 2.5 \text{ mg/dL}$

¹Therapeutic levels of anti-coagulation are permitted if clinically indicated, as per section 3.2.15. Thus PT/INR may be >1.3 if therapeutically anti-coagulated.

3.1.9 The effects of INCB039110, dabrafenib, and trametinib on the developing human fetus are unknown. For this reason, women of child-bearing potential must have a *negative serum pregnancy test within 14 days prior to registration and agree to use effective contraception* (barrier method of birth control, or abstinence; hormonal contraception is not allowed due to drug-drug interactions which can render hormonal contraceptives ineffective) *from 14 days prior to registration*, throughout the treatment period, and for 4 months after the last dose of study treatment. Should a woman become pregnant or suspect she is pregnant while she is participating in this study, she should inform her treating physician immediately.

Based on studies in animals, it is also known that dabrafenib may cause damage to the tissue that makes sperm. This may cause sperm to be abnormal in shape and size and could lead to infertility, which may be irreversible.

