5.4.2 Dabrafenib

Because there is a potential for interaction of dabrafenib with other concomitantly administered drugs through the cytochrome P450 system, the case report form must capture the concurrent use of all other drugs, over-the-counter medications, or alternative therapies. The Principal Investigator should be alerted if the patient is taking any agent known to affect or with the potential to affect selected CYP450 isoenzymes. Appendix B is a patient information sheet that can be used for this specific protocol and presented to the patient.

Dabrafenib mesylate is a substrate for CYP 3A4, 2C8, p-glycoprotein (Pgp), and breast carcinoma resistance protein (Bcrp). Strong inhibitors/inducers of these enzymes and transporters are prohibited for eligibility and during the study.

Mild or moderate inhibitors/inducers of CYP 3A4, 2C8, Pgp, and Bcrp should be used with caution as dabrafenib serum concentrations may be altered. Because the lists of these agents are constantly changing, it is important to regularly consult a frequently-updated list such as <http://medicine.iupui.edu/clinpharm/ddis/table.aspx>; medical reference texts such as the Physicians' Desk Reference may also provide this information.

Dabrafenib may induce CYP 3A4, 2B6, and possibly 2C8/9 and 2C19. Use concomitant medications that are substrates of these isoenzymes with caution as there may be loss of efficacy. Substitute with other medications that are not affected if possible.

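### Appendix E Table 2 lets oral contraceptives be co-administered with monitoring, although criterion 3.1.9 rules out hormonal contraception for women of child-bearing potential throughout treatment

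*Combined protocol and SAP*

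**What the plan says.** Section 3.1.9 requires women of child-bearing potential to use a barrier method or abstinence. It states that "hormonal contraception is not allowed due to drug-drug interactions which can render hormonal contraceptives ineffective". The obligation starts 14 days before registration and continues "throughout the treatment period, and for 4 months after the last dose of study treatment".

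Appendix E, 1.3 (Medications to be Used with Caution) covers drugs whose exposure dabrafenib may lower by enzyme induction. It says: "If co-administration of these medications is necessary, investigators should monitor subjects for loss of efficacy or consider substitutions of these medications". Table 2 lists examples. The Miscellaneous row of its block of induction-sensitive substrates includes "disopyramide, leflunomide, methohexitol, oral contraceptives, quinine, ranitidine", and the heading of that block instructs: "Monitor subjects for loss of efficacy or substitute with another medication". The table makes no exception for contraceptives and does not refer to 3.1.9.

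Section 5.4.2, on the same class of substrates, advises caution and adds: "Substitute with other medications that are not affected if possible".

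Appendix E, 1.2 has its own list, introduced by "The following medications or non-drug therapies are also prohibited while on treatment in this study". Hormonal contraceptives are not on it.

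**The concern.** Although 3.1.9 sits among the eligibility criteria, it governs conduct for the whole treatment period. Appendix E is where a coordinator or pharmacist would naturally look when a co-medication question arises mid-treatment. There, oral contraceptives appear in the caution tier, not the prohibited tier.

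What is at stake is patient safety. Section 2.3.2.4 (Embryofetal toxicity) says that dabrafenib and trametinib, alone or together, can harm the fetus, and cites rat and rabbit findings. Section 3.2.8 treats all three study drugs as possibly teratogenic or abortifacient. A woman who stayed on an oral contraceptive under the Table 2 instruction, and relied on it, would be using a method the protocol itself considers unreliable with this treatment. No endpoint, DLT rule, sample size or analysis is affected.

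**Working it through.** No calculation applies, so the check compares the texts directly.

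**1. Where the two rules overlap.**

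| | Section 3.1.9 | Appendix E 1.3 and Table 2 |
|---|---|---|
| Who | Women of child-bearing potential | All participants |
| What | Hormonal contraception | Oral contraceptives |
| When | 14 days before registration to 4 months after last dose | While given together with study treatment |
| Rule | Not allowed | Caution: monitor or substitute |

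The overlap is the treatment period. Table 2 gives no permission for the 4 months after the last dose. Appendix E 1.1 asks to be told of "any medication taken from the time of screening until 30 days after the last dose of study treatment", but that sets a reporting period and permits nothing.

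**2. The two routes in Table 2.** The instruction offers alternatives.
- *Substitute:* replacing the oral contraceptive with a barrier method or abstinence satisfies both texts.
- *Monitor:* the oral contraceptive continues, which 3.1.9 does not allow for contraception.

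The conflict is therefore confined to the second route.

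**3. Whether the monitoring route can be carried out.** For warfarin, Appendix E 1.3 names the measure, PT/INR. For a contraceptive it names none, and in practice loss of efficacy shows itself as pregnancy. The Section 10 calendar marks the serum pregnancy test at baseline and Cycle 1 Day 1 only. Footnote c waives the Day 1 test if one was done within 72 hours of the first dose. Nothing is scheduled in later cycles or at the end-of-treatment visit. A failure would be found only after the fetus might already have been exposed.

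**4. Whether another list closes the gap.**
- Section 3.2.16 (prohibited medications): hormonal contraceptives not named.
- Appendix E 1.2, bullets: not named.
- Appendix E Table 1: not named.

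That is 0 of 3 prohibited lists, against 1 of 1 caution list (Table 2) that names oral contraceptives. Table 1 and the matching table within 3.2.16 cover strong CYP inhibitors and inducers that alter dabrafenib levels, so absence from those is expected. The absences that matter are from the general bullets in 3.2.16 and Appendix E 1.2. Section 5.4.2 leans towards substitution but qualifies it, so it does not remove the monitoring route.

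**5. Whether the interaction is a real one.** Section 2.3.2 reports that dabrafenib 150 mg twice daily for 15 days lowered the AUC of midazolam, a CYP3A4 substrate, by 74%, leaving 100% − 74% = 26%. The protocol gives no corresponding figure for an oral contraceptive, but 3.1.9 already draws the conclusion that hormonal methods can fail.

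**6. Whether the appendix matches the body elsewhere.** Fluconazole is prohibited in 3.2.16 but appears under caution in Appendix E Table 2. The appendix was evidently not fully reconciled with the main text.

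**The case against.** The best defence is that the two texts answer different questions. Section 3.1.9 says which contraceptive method counts. Table 2 is a general interaction list whose message, that induction may cost efficacy, is the very reason 3.1.9 gives for its rule. Table 2 never says an oral contraceptive meets the contraception requirement. A woman who uses a barrier method and takes an oral contraceptive for another indication arguably complies with both. Section 3.1.9 is also the more specific rule, and the participant must agree to it before enrolment. Finally, Appendix B, the SPM and the consent form were not available for this review, and any of them may repeat the ban.

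Much of this stands, and it limits the weight of the point. Substitution is compliant, non-contraceptive use may be legitimate, and it cannot be claimed that the ban appears nowhere else in the trial's materials. But Table 2 does not confine itself to non-contraceptive use, and the available text states no order of precedence between 3.1.9 and Appendix E. A reminder in another document would leave the monitoring instruction in force as written.

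**Conclusion.** The concern holds. For contraceptive use during treatment, Appendix E 1.3 and Table 2 offer a route that 3.1.9 forbids, and the protocol schedules no test by which that route could be followed safely. This is a wrong instruction with a safety consequence and should be corrected. It does not call the trial's design into question.

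Its reach is small. Harm requires a site that relies on Appendix E alone for an on-treatment co-medication decision and chooses to monitor, while 3.1.9 continues to require barrier or abstinence. How many women could be affected cannot be estimated, because the documents do not give the number of child-bearing potential. The conclusion assumes that Table 2 means oral contraceptives without restriction, as it is written. Confidence in the textual conflict is high.

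**What to change.** In the next amendment:

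1. Remove oral contraceptives from the caution row of Appendix E Table 2.
2. Add a line to Appendix E 1.2 stating that hormonal contraceptives are not allowed for contraception, and name 3.1.9 as the governing rule, including its 4-month period after the last dose.
3. If use for a non-contraceptive indication is meant to be permitted, say so, and state that it does not count as contraception.

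The cost is one table entry removed, one line added and one cross-reference, with the optional clarification in item 3. No additional patients, visits or staff are needed. When making the change, check that Appendix B, the SPM and the consent form say the same.
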